4.10.3.8 Average Count of Salbutamol Puffs Per Day (Days 1-85)

Use of salbutamol as a rescue medication will be documented in a medication diary and recorded in the eCRF. Rescue medication use should be recorded as the number of doses per day, where each puff of salbutamol is one dose.

The average count of rescue salbutamol puffs per day will be calculated for each monthly interval by dividing the total salbutamol puff counts for each of the 3 monthly intervals by the total number of days on study for that month.

Average count of rescue salbutamol puffs per day = Total salbutamol puff counts / Number of non-missing days during each defined interval

where the "number of non-missing days" is the actual number of days in the interval whilst receiving study treatment.

If a subject withdraws from study treatment early, only the number of days on treatment in the interval will be included in the count of non-missing days and rescue medication information collected after withdrawal will not be included in the calculations.

The baseline average count of rescue salbutamol puffs per day will be calculated using the last 7 daily entries recorded within 14 days prior to randomization on Day 1.

The average count of salbutamol puffs per day will be analyzed using the same MMRM analysis described for the primary analysis of the primary endpoint with the time variable Month (1, 2, 3) replacing Visit.

The average count of salbutamol puffs per day for the study (Days 1-85) will be estimated from the model-derived average of each of the 3 months using an appropriate estimate statement as well as the LS mean differences, 95% CI and associated 2-sided p-values.

Estimates for each one month period (Months 1, 2 and 3) will also be reported.

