## 6.6 Mitigation in the event of a public health emergency

In the event of any circumstances impacting the ability of enrolled subjects to attend for scheduled visits at the investigator site, such as travel restrictions imposed due to COVID-19, investigators must notify the Sponsor and make the necessary arrangements to ensure the safety of their enrolled subjects. They should also evaluate whether their subjects should continue in the clinical trial. Those that have not been randomized yet should be withdrawn from the study.

Where it is possible for randomized subjects to continue, the following operational contingencies will be implemented:

- Study medication, rescue medication, and other study supplies such as diary cards will be sent to the subject's residence to ensure sufficient quantities are available.
- Virtual visits will be conducted by telephone in place of the scheduled visits, whereby the investigator will perform those procedures specified in Section 6.2 that are feasible to be performed by telephone, such as questioning on adverse events, concomitant medications, and rescue medication use, completion of TDI, etc).
- Subjects will be reminded to bring (or send) all used and unused study medication, rescue medication, and diary cards to the site as soon as they are able after travel restrictions have been lifted.

Protocol deviations arising under such circumstances (eg, missed or delayed visits, assessments not performed, etc) will be clearly documented in the CRF and the reasons will be collected.

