### 7.4.3 Rescue Medication Usage

#### 7.4.3.1 Average Count of Salbutamol Puffs Per Day (Days 1-85)

The average count of rescue salbutamol puffs per day will be calculated for each monthly interval by dividing the total salbutamol puff counts for each of the 3 monthly intervals by the total number of days on study for that month.

The average count of salbutamol puffs per day will be analyzed using the same MMRM analysis described for the primary analysis of the primary endpoint with the time variable Month (1, 2, 3) replacing Visit. The average count of salbutamol puffs per day for the study (Days 1-85) will be estimated from the model-derived average of each of the 3 months using an appropriate contrast statement as well as the LSmean differences, 95% CI and associated 2-sided p-values.

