#### 4.10.1.3 Handling Missing Data

Missing or unavailable data will be queried by Data Management. Data that remains missing will be identified in summaries and analyses of that data item.

For any subject who withdraws prematurely from study treatment, all available data up to the time of discontinuation of study treatment will be considered for inclusion in the analyses. An Early Termination visit will occur as soon as possible after their last dose of study drug.

The following graphical representations are examples of plots that may be used to explore the data and help to explain any dropout patterns. The actual plots used will be dependent on the final dropout rate/pattern for the study:

- Kaplan-Meier plots of time to discontinuation of study treatment split by treatment group.
- Kaplan-Meier plots of time to discontinuation of study treatment split by treatment group and reason for discontinuation (e.g. Lack of Efficacy, Adverse Events).
- Kaplan-Meier plots of time to discontinuation of study treatment split by treatment group and relationship to public health emergency (related, not related).

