#### 4.10.3 Secondary Efficacy Variables

In all the secondary efficacy analyses the FAS population will be used and missing data will not be imputed and will be assumed to be missing at random (MAR) unless otherwise stated. If a public health emergency prevents data from being measured or requires data to be assessed remotely via a virtual visit, then information on the reasons and the data impacted will be recorded in the CRF.

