4.10.3.9 Percentage of Salbutamol Rescue Free 24h Periods (Days 1-85)

A 24h rescue-free period is defined as a day without a "yes" for rescue use per the daily diary.

The percentage of salbutamol rescue free 24h periods will be calculated for each monthly interval by dividing the number of 24h rescue-free periods for each of the 3 monthly intervals by the total number of days on study for that month.

Percentage of salbutamol rescue free 24h periods = Number of 24h rescue-free periods / Number of non-missing days, and multiplying by 100 during each defined interval,

where the "number of non-missing days" is the actual number of days in the interval whilst receiving study treatment.

If a subject withdraws from study treatment early, only the number of days on treatment in the interval will be included in the count of non-missing days and rescue medication information collected after withdrawal will not be included in the calculations.

The baseline percentage of salbutamol rescue free 24h periods will be calculated using the last 7 daily entries recorded within 14 days prior to randomization on Day 1.

The percentage of salbutamol rescue free 24h periods will be analyzed using the same MMRM analysis described for the primary analysis of the primary endpoint with the time variable Month (1, 2, 3) replacing Visit.

The average percentage of salbutamol rescue free 24h periods for the study (Days 1-85) will be estimated from the model-derived average of each of the 3 months using an appropriate estimate statement as well as the LSmean differences, 95% CI and associated 2-sided p-values.

Estimates for each one month period (Months 1, 2 and 3) will also be reported.

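### The rescue-use denominator includes blank diary days, so as written they score as zero puffs and rescue-free; both rescue models also keep baseline FEV1 instead of baseline rescue use

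*SAP*

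**What the plan says.** **Denominator.** SAP 4.10.3.8 gives monthly average use as "Total salbutamol puff counts / Number of non-missing days during each defined interval". The line below the formula says the number of non-missing days "is the actual number of days in the interval whilst receiving study treatment". SAP 4.10.3.9 uses the same label and the same definition for the rescue-free percentage. The lead sentence in each SAP section, and Protocol 7.4.3.1 and 7.4.3.2, divide instead "by the total number of days on study for that month". The only days explicitly removed are those after withdrawal from treatment.

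**Rescue-free day.** SAP 4.10.3.9 states: "A 24h rescue-free period is defined as a day without a 'yes' for rescue use per the daily diary". A recorded *no* is not required.

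**Missing data.** For secondary endpoints SAP 4.10.3 says "missing data will not be imputed and will be assumed to be missing at random (MAR) unless otherwise stated". SAP 4.10.1.3 limits imputation to the sensitivity analyses of the primary endpoint and adds: "Data that remains missing will be identified in summaries and analyses of that data item".

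**Baseline.** Both rescue baselines are calculated "using the last 7 daily entries recorded within 14 days prior to randomization on Day 1".

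**Model.** Both endpoints use the primary MMRM with Month in place of Visit, and no other substitution is stated. The primary MMRM (SAP 4.10.2.1) adjusts for baseline FEV1 and its interaction with time.

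**The concern.** The label and the definition describe different quantities. Under the definition, a treatment day with no diary entry adds nothing to the puff total, stays in the denominator, and qualifies as rescue-free because it carries no *yes*. That is an implicit favourable imputation in a plan that says secondary data are not imputed. Baseline is built from recorded entries only, so baseline and on-treatment values treat blank days differently within one section.

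If use on blank days resembles use on recorded days, equal blank rates pull the treatment difference towards zero. Unequal rates can enlarge, hide or create a difference in either direction. Two programmers could also derive different values from the same text.

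The covariate is a separate and lesser matter. The SAP replaces baseline FEV1 explicitly for FVC (4.10.3.1) and TDI (4.10.3.6) and uses baseline SGRQ for SGRQ (4.10.3.4, 4.10.3.5). It derives a rescue baseline but gives it no stated role in either rescue model. The cost is precision, not bias.

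**Working it through.** The documents give no design figure for the rescue endpoints, so there is nothing of the plan's to reproduce. Every input below is an assumption.

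**One subject-month.** Take 28 treatment days, 21 completed diary days, 84 puffs, and 7 completed days without use.

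| Reading | Puffs/day | Rescue-free |
|---|---|---|
| As written | 84/28 = 3.0 | (7+7)/28 = 50.0% |
| Denominator corrected only | 84/21 = 4.0 | 14/21 = 66.7% |
| Denominator and rescue-free rule corrected | 84/21 = 4.0 | 7/21 = 33.3% |

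Correcting the denominator alone makes the percentage worse, so both definitions must change.

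**Group level.** Let m be the share of blank treatment days, with blanks unrelated to use. As written:

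- expected puffs = true × (1 − m)
- expected rescue-free % = true × (1 − m) + 100m

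Per percentage point of imbalance, at 3.0 puffs/day and 40% rescue-free:

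- 0.01 × 3.0 = 0.03 puffs (0.01 to 0.05 for 1 to 5 puffs/day)
- 0.01 × (100 − 40) = 0.6 points (0.8 to 0.4 for 20% to 60% rescue-free)

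Scenarios, with placebo at 3.0 puffs and 40%. Where there is a true benefit, revefenacin is at 2.5 puffs and 50%.

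| True benefit | Blanks, placebo / revefenacin | Apparent benefit, puffs | Apparent benefit, points |
|---|---|---|---|
| None | 15% / 5% | 2.55 − 2.85 = −0.30 | 43 − 49 = −6 |
| None | 5% / 15% | 2.85 − 2.55 = +0.30 | 49 − 43 = +6 |
| 0.5 puffs, 10 points | 10% / 10% | 2.70 − 2.25 = 0.45 | 55 − 46 = 9.0 |
| 0.5 puffs, 10 points | 15% / 5% | 2.55 − 2.375 = 0.175 | 52.5 − 49 = 3.5 |
| 0.5 puffs, 10 points | 5% / 15% | 2.85 − 2.125 = 0.725 | 57.5 − 43 = 14.5 |

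**The opposite assumption.** If every blank day was truly free of use, the literal rule is correct and averaging over recorded days overstates use: at 10% blank, 3.0/0.9 = 3.33.

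**Covariate.** Let r be the correlation between baseline and on-study use, and suppose baseline FEV1 explains little of rescue use.

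- Raw outcome: the SE with the rescue baseline in the model, relative to without it, is √(1 − r²) = 0.866, 0.800 and 0.714 at r = 0.5, 0.6 and 0.7. That is a cut of 13% to 29%.
- Change from baseline, if that was meant: relative to an unadjusted change score the ratio is √((1 + r)/2) = 0.866, 0.894 and 0.922, a cut of 13% down to 8%. SAP 3.2.1 lists the rescue endpoints without a change-from-baseline prefix, so the raw outcome is the likelier reading.

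**Short baselines.** With an assumed daily intraclass correlation of 0.5, the reliability of a mean of k entries is 0.5k/(1 + 0.5(k − 1)): 0.800 for 4 entries and 0.875 for 7. The correlation is then multiplied by √(0.800/0.875) = 0.956, and the 13–29% cut becomes 12–26%. A short baseline is still worth using.

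**The case against.** The label may show the real intention. Non-missing days can be read as recorded days, with the next line meant only to stop the count at treatment withdrawal, which is all the following paragraph discusses. That is plausible, but the definition, the lead sentences and the protocol all point to every day, and the rescue-free rule would still count blanks.

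The endpoint wording might also be the exception that SAP 4.10.3 allows. It never mentions missing entries, though, and the restriction on imputation in SAP 4.10.1.3 has no such escape. The promise there to identify missing data is weaker support, because blanks can be reported under either denominator.

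Materiality is assumed throughout. Nothing in the documents says blanks will be common or will differ by arm in a double-blind trial, and with equal rates the effect is modest attenuation. Diaries are reviewed at clinic visits and missing data are queried. These steps may reduce blanks but set no rule for those that remain. In a public health emergency (Protocol 6.6) visits move to telephone and subjects bring or send "diary cards to the site as soon as they are able after travel restrictions have been lifted". That route is not arm-specific.

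On baseline entries, the protocol synopsis hands out the diary after Visit 2, while Table 1-1 and section 6.1.1 dispense it at Visit 1, nominally Day −14. A run as short as four days therefore needs Visit 1 at the end of its window, for example combined with Visit 2 on Day −4. It is an edge case, but no rule covers it.

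On the covariate, the Appendix 6.1 sample code is not in the text available for review and might name a different one. If change from baseline was meant, the rescue baseline would enter through the outcome and the gain would be the smaller figure above.

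**Conclusion.** The concern holds on the text. As written, a blank on-treatment diary day becomes zero puffs and a rescue-free day, contrary to the plan's own no-imputation rule and to its entry-based baseline. The contradiction itself rests on no assumption. The size of any distortion does: it needs a blank-day rate and a level of use, and blanks that resemble recorded days. Small, balanced blank rates would do little harm; a 10-point imbalance could match or exceed half of an assumed 0.5-puff benefit.

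The covariate point also holds, as lost precision only, and its size depends on an assumed correlation. Both matters concern secondary endpoints reported with confidence intervals and p-values. They should be corrected, but they do not affect the primary analysis.

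**What to change.** In SAP 4.10.3.8 and 4.10.3.9:

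- Define the denominator as on-treatment days with a diary entry for rescue use.
- Count a day as rescue-free only with a recorded *no* or zero puffs.
- Pre-specify a minimum number of entries per month, below which that month is missing. The sponsor should choose the number without sight of treatment assignment.
- Report blank days by arm and month.
- Keep the all-treatment-days version as a sensitivity analysis, for the case that subjects left use-free days blank.
- Name the covariate: replace baseline FEV1 and its time interaction with the matching rescue baseline and its month interaction.
- Where fewer than seven baseline entries exist, use those available so that subjects are not dropped.

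List the denominator change in SAP 4.13, since it departs from Protocol 7.4.3.1 and 7.4.3.2; Protocol section 7 allows the SAP to do this. If the database is already locked, SAP 4.13 places such changes in the study report.

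The cost is wording, with no new data collection, provided the eCRF distinguishes a blank from a zero or *no*; the eCRF was not available to check. Some sparse subject-months will become missing, baselines built on few entries will be noisier, and recorded-day averages will overstate use if blanks really were use-free.

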4.10.3.9 Percentage of Salbutamol Rescue Free 24h Periods (Days 1-85)

A 24h rescue-free period is defined as a day without a "yes" for rescue use per the daily diary.

The percentage of salbutamol rescue free 24h periods will be calculated for each monthly interval by dividing the number of 24h rescue-free periods for each of the 3 monthly intervals by the total number of days on study for that month.

Percentage of salbutamol rescue free 24h periods = Number of 24h rescue-free periods / Number of non-missing days, and multiplying by 100 during each defined interval,

where the "number of non-missing days" is the actual number of days in the interval whilst receiving study treatment.

If a subject withdraws from study treatment early, only the number of days on treatment in the interval will be included in the count of non-missing days and rescue medication information collected after withdrawal will not be included in the calculations.

The baseline percentage of salbutamol rescue free 24h periods will be calculated using the last 7 daily entries recorded within 14 days prior to randomization on Day 1.

The percentage of salbutamol rescue free 24h periods will be analyzed using the same MMRM analysis described for the primary analysis of the primary endpoint with the time variable Month (1, 2, 3) replacing Visit.

The average percentage of salbutamol rescue free 24h periods for the study (Days 1-85) will be estimated from the model-derived average of each of the 3 months using an appropriate estimate statement as well as the LSmean differences, 95% CI and associated 2-sided p-values.

Estimates for each one month period (Months 1, 2 and 3) will also be reported.

#### 4.11 Safety Evaluation

Safety analyses include extent of exposure, adverse event (AE), laboratory test, vital signs, electrocardiogram (ECG) and physical examination.

Safety endpoints will be summarized using the Safety Analysis Set (SS) population. All safety analyses will be presented by treatment group.

There are no planned statistical analyses for the comparison of treatments for the safety endpoints.

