##### **3.1.2 Secondary Objectives**

The secondary objectives of the study are as follows:

- To confirm the safety of revefenacin inhalation solution 175 mcg administered once daily via nebulization for 12 weeks compared to placebo in a population of Chinese subjects with moderate to very severe COPD
- To characterize the effect of revefenacin inhalation solution 175 mcg on patient reported outcomes compared to placebo in a population of Chinese subjects with moderate to very severe COPD.
- To collect PK samples for population PK analysis of revefenacin inhalation solution 175 mcg in a population of Chinese subjects with moderate to very severe COPD.

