## 7.5 Safety Endpoints

Safety endpoints will be summarized using the SS population. There are no planned analyses for the comparison of treatments for the safety endpoints.

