### 7.5.1 Adverse Events

Adverse events will be summarized and listed. All AEs that occur after the first dose of study medication through 30 days after the last dose will be considered to be treatment emergent AEs. The number and percentage of subjects with at least one treatment emergent AE will be presented by treatment group and events further summarized by maximum severity and relationship to study medication. Summary statistics (N, %) of AEs of special interest will be also be separately tabulated.

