### 7.5.2 Acute Exacerbations of COPD (AECOPD)

A summary of acute exacerbations of COPD reported with an AE preferred term of COPD will be descriptively summarized by severity. Exacerbation data will be summarized (N, %) for all exacerbations; moderate and severe exacerbations; and severe only exacerbations.

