### 7.5.3 Other Safety Endpoints

Descriptive statistics will be provided for the following safety data. No inferential analysis of this safety data is planned. Any ECG, BP, and pulse rate abnormalities of potential clinical concern will be described.

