## 2.2 Secondary Objectives

The secondary objectives of the study are:

- To confirm the safety of revefenacin 175 mcg administered once daily via nebulization for 12 weeks compared to placebo in a population of Chinese subjects with moderate to very severe COPD.
- To characterize the efficacy of revefenacin 175 mcg on patient reported outcomes compared to placebo in a population of Chinese subjects with moderate to very severe COPD.
- To collect pharmacokinetics (PK) samples for population PK analysis of revefenacin 175 mcg in a population of Chinese subjects with moderate to very severe COPD.

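### The safety objective is to confirm safety against placebo, but the planned output gives no between-arm estimate or interval, so it cannot say how much excess risk is excluded

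*SAP*

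**What the plan says.** The first secondary objective is both confirmatory and comparative. Protocol 3.1.2 reads "To confirm the safety of revefenacin inhalation solution 175 mcg administered once daily via nebulization for 12 weeks compared to placebo", and SAP 2.2 repeats it: "To confirm the safety of revefenacin 175 mcg administered once daily via nebulization for 12 weeks compared to placebo".

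The analysis sections are descriptive. Protocol 7.5 states: "There are no planned analyses for the comparison of treatments for the safety endpoints". SAP 4.11 says the same: "There are no planned statistical analyses for the comparison of treatments for the safety endpoints". For vital signs, ECG and laboratory data, Protocol 7.5.3 adds: "No inferential analysis of this safety data is planned".

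The outputs match those statements:

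- **Adverse events (Protocol 7.5.1):** "The number and percentage of subjects with at least one treatment emergent AE will be presented by treatment group". SAP 4.11.2 and 4.11.3 list the corresponding tables, including serious events and events leading to discontinuation.
- **Exacerbations (Protocol 7.5.2):** "Exacerbation data will be summarized (N, %) for all exacerbations; moderate and severe exacerbations; and severe only exacerbations".
- **Antimuscarinic events (SAP 4.11.2):** incidence only.

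The sample size (Protocol 7.1, SAP 4.12) rests on trough FEV1 alone.

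**The concern.** An objective to confirm something against a comparator leads the reader to expect a comparative estimate. Here the reader gets two columns of percentages and no measure of how uncertain the gap between them is. Similar-looking columns at about 160 per arm are compatible with a sizeable excess on revefenacin for uncommon events, and nothing in the planned tables shows how large that excess could be.

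The objectives list makes the mismatch plain. Patient-reported outcomes are only to be characterized, yet SAP 4.10.3.4 to 4.10.3.7 give them between-arm estimates with 95% intervals. Safety has the stronger verb and receives no between-arm estimate.

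What is at stake is the wording of the safety conclusion in the study report. A statement that safety was confirmed would have no stated precision behind it. No efficacy result is affected.

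**Working it through.** **1. The plan's own sizing.** Inputs from Protocol 7.1 and SAP 4.12: difference 100 mL, SD 245 mL, two-sided 5%, at least 90% power, 20% dropout.

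- Normal approximation: n per arm = 2 × [(1.960 + 1.282) × 245 / 100]² = 126.1, rounded up to 127.
- With the t distribution, 127 per arm gives 89.98% power and 128 per arm gives 90.2%, so 128 per arm (256 in total) reproduces.
- Dropout: 256 / (1 − 0.20) = 320, or 160 per arm.

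The sizing is correct for FEV1. Neither document sizes or sets a precision target for any safety endpoint.

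**2. What equal columns would leave open.** The planned n is 160 per arm (Protocol synopsis). The emergency cap of 428 (Protocol 7.1) gives 428 / 2 = 214 per arm. I take all randomized subjects as dosed, so these are also the safety-set sizes. The documents give no placebo event rates for this setting, so 2%, 5% and 10% are assumed as a range.

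For an observed proportion p in n subjects, with z = 1.96, the Wilson limits are

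l, u = [p + z²/(2n) ± z √(p(1 − p)/n + z²/(4n²))] / (1 + z²/n).

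When both arms show the same p, the Newcombe 95% interval for the risk difference is 0 ± √[(u − p)² + (p − l)²].

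| n per arm | Observed rate in both arms | Wilson l, u (%) | Calculation | Upper limit of difference (points) |
|---|---|---|---|---|
| 160 | 2% | 0.704, 5.547 | √(3.547² + 1.296²) | +3.8 |
| 160 | 5% | 2.555, 9.555 | √(4.555² + 2.445²) | +5.2 |
| 160 | 10% | 6.249, 15.626 | √(5.626² + 3.751²) | +6.8 |
| 214 | 2% | 0.804, 4.889 | √(2.889² + 1.196²) | +3.1 |
| 214 | 5% | 2.793, 8.795 | √(3.795² + 2.207²) | +4.4 |
| 214 | 10% | 6.660, 14.751 | √(4.751² + 3.340²) | +5.8 |

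Two percent of 160 is 3.2 subjects. The nearest whole count, 3 against 3 (1.9%), gives ±3.7 points.

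**3. Reading the result.** Identical 2% columns at 160 per arm would leave an excess of up to 3.8 points unexcluded, which is larger than the rate itself. At 5% the unexcluded excess (5.2) is about the size of the rate. At 10% it is smaller than the rate (6.8). The planned tables would show none of these limits.

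**The case against.** The strongest reply is that descriptive safety reporting is usual in a trial sized for efficacy, and that both documents say so consistently. Protocol 2.2 also frames the study as a bridge to existing data: 395 subjects on 175 mcg in studies 0126 and 0127, and 335 in the 52-week study 0128. On that reading, confirm means consistent with a known profile, and was never meant as exclusion of harm from this trial alone. Much of this stands: no test is needed, and nothing is wrong with descriptive tables as such. But the objective as written is relative to placebo in Chinese subjects. That comparison comes from this trial, and study 0128 was tiotropium-controlled.

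A reader might infer three stronger points, which the documents do not support:

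- **That safety will be declared because no difference is noticed**, as if a non-significant result were proof of safety. Neither document states such a rule. There is no safety hypothesis, margin or success criterion.
- **That the plan forbids the comparison or throws the placebo data away.** It says none is planned. The counts are tabulated by arm, and an interval can be computed from them. What is missing is a planned display.
- **That the trial fails because it would usually miss a doubling of risk.** At 160 per arm, exact Fisher power for a doubling is about 10% from 2%, 32% from 5% and 66% from 10%. But the plan does not run that test and the fix below does not add it. The figures rest on assumed placebo rates, and by the last of them a doubling would be detected more often than missed.

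It is also fair to say that wide intervals will not turn the result into a confirmation. That is why the verb should change as well.

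**Conclusion.** The mismatch is real and modest. A comparative, confirmatory safety objective is paired with output that contains no comparative estimate, so the report cannot say how much excess risk the data exclude. With equal observed rates of 2%, 5% or 10%, the excess not excluded at the 95% level is 3.8, 5.2 or 6.8 points at 160 per arm, and 3.1, 4.4 or 5.8 points at 214 per arm.

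These sizes assume 1:1 allocation, all randomized subjects dosed, simple proportions of subjects with an event, and event rates that I chose as a range. The defect lies in the objective's wording and a missing display. It does not lie in the absence of p-values, and the documents do not show that a false safety claim is planned.

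**What to change.** 1. In SAP 4.11 and Protocol 7.5, replace the no-comparison sentence with text along these lines: *Between-arm risk differences (revefenacin minus placebo) with 95% Newcombe confidence intervals will be presented descriptively for subjects with any TEAE, any serious TEAE, any TEAE leading to discontinuation, any AECOPD, any moderate or severe AECOPD, and any antimuscarinic event. No hypothesis tests will be performed.*
2. State that each upper limit will be reported as the excess risk not excluded, with no pass/fail threshold. The plan has no margin to compare it with, and one should not be implied.
3. In Protocol 3.1.2 and SAP 2.2, change the verb in the safety objective from confirm to characterize, keeping the comparison with placebo. Align the same wording in the protocol's background section and the SAP introduction.

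The cost is one table. Its numerators are already planned by arm, except perhaps a single count of subjects with any antimuscarinic event. It needs no new data or visits and uses no alpha. The downside is a handful of unadjusted intervals, which should be labelled descriptive, a less absolute safety statement, and a small edit to protocol text as well as the SAP.
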